⁴⁴ health behavior adherence (e.g., smoking cessation and risky drinking),⁴⁵⁻⁴⁷ and outcomes (e.g., lung cancer death rates and sobriety). A-CHESS is consistent with respected health behavior change models such as self-determination theory (SDT)⁴⁸ and Marlatt's Cognitive Behavior model⁴⁹ of relapse prevention. In a randomized trial (N=349), patients using A-CHESS, compared to those in the control group, reported 51% fewer risky drinking days in the prior 30 days at the 4-, 8-, and 12-month follow-ups (mean of 1.39 days in A-CHESS vs. 2.75 days per month in TAU, $p = .003$). Rates of alcohol abstinence were significantly higher among A-CHESS patients at 8 months (78% vs. 67%) and 12 months (79% vs. 66%).⁵⁰ The A-CHESS app includes educational materials, discussion groups, links to SUD resources and weekly self-monitoring for patients. The CHESS platform has also been an effective method for clinicians to interact with their patients.⁵¹ A-CHESS provides a report for clinicians that delivers to the clinician team information about worrisome changes in symptoms collected from the patient during self-monitoring of risk-related items (i.e., sleeping problems, depression, urge, risky situation and relationship troubles).⁵² A-CHESS contacts the clinical team by email, phone, or fax (according to clinician preference) whenever a threshold symptom is reported. The alert was intended to quickly bring clinician attention to emerging symptoms.

Technology like A-CHESS is a potential game changer: it can provide recovery supports 24 hours a day, 7 days a week and can be customized to individual needs. **This research will test a technology adoption framework to increase use of the A-CHESS smartphone app.** A supplemental study will help understand how A-CHESS may help patients manage increased levels of anxiety and loneliness during the COVID-19 pandemic.

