Patient use of A-CHESS app (same for Control and Intervention) – At the first use of the A-CHESS app, the patient will use an automated A-CHESS set up. The set-up tool will train patients to use A-CHESS and customize it (e.g. by sources of support [e.g. family], and contacts who detract from recovery [e.g. friends who use illegal drugs]). A-CHESS will be updated monthly with activities for the healthy event calendar, changes to therapeutic goals and recovery plan (e.g., self-help groups, medication, home-work-education responsibilities), and high-risk locations to avoid. Patients can use video tutorials to practice A-CHESS services and experience how A-CHESS can help them

With subsequent use of the A-CHESS app patients will be asked how they are doing and about their recent alcohol and drug use. These questions will be sent weekly on the A-CHESS system and will take about 2-4 minutes to complete. All questions are voluntary. Patients are free to refuse to answer any questions they are uncomfortable with. However, by answering the weekly questions about their recent alcohol and drug use A-CHESS can send the patient information to help them in their recovery. In addition, data based on their responses will be accessible to his/her clinical team via the *Counselor Dashboard* so the clinic team can provide needed support. This sensitive health information is being collected and shared via the *Counselor Dashboard* to allow clinicians to be better informed and provide treatment more responsively based on their patients' needs as they deal with addiction and other serious health issues. All patients will be reminded that they are under no obligation to participate in this study, can withdraw from the study at any time, and in no way will their health care be affected by their participation in this study.

Intervention: NIATx-TI with Product Training/On-line Support – For SUD organizational sites in the Intervention arm, the NIATx TI framework includes the product training as well as a pre-implementation (planning) phase and a post-implementation (problem-solving) phase. A NIATxTI coach (who is also an A-CHESS product trainer) will provide the training for this arm. The coach will also assist the organizations with applying the NIATx-TI framework. **Figure 1** presents the steps in the NIATx-TI Framework.

[figure not shown]
Pre-implementation (Planning) Phase

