% who download A-CHESS app and frequency of A-CHESS use in days	Gustafson et al. ⁵⁰	A-CHESS Server - Monthly (Ms 11 - 47) IDPH – Monthly (Ms11 - 47)
Adoption		
% Counselor Using A-CHESS	Knight et al. ⁵⁹	Organizational Survey & A-CHESS Logs
Effectiveness		
Retention (Length of Stay)	Simpson et al. ⁶¹	IDPH- Ms 11 - 50
Maintenance		
Finance Resource Availability	Klein ⁶²	Organizational Survey – Ms 12, 30

Measurement	Measure Source	Data Source/Frequency (for Cohort 1)
A-CHESS Implementation Fidelity	Developed for this trial	Staff Survey – Ms 12, 30
Organizational Change Manager (OCM)	Gustafson et al. ⁶³	Staff Survey – Ms 11, 12, 30
Patient COVID-19 Survey		
Patient socio-demographic and descriptive characteristics: age, race/ethnicity, sex, gender, sexual orientation, education, marital status, income, housing, family size, employment status, health insurance	PhenX repository	Patient COVID-19 Survey – once during March 2021
Criminal justice history	Justice Community Opioid Involvement Network	
Alcohol Use Disorder Severity	Saunders et al.; Babor et al.	
Substance Use Disorder Severity	Skinner	
Loneliness	Hays & DiMatteo	
Anxiety	Cella et al.	
Substance use disorder recovery strengths	Vilsant et al.	
COVID-19 risk and protective behaviors and impact on daily living	Adapted from several COVID-19 surveys	

Qualitative Interviews: Qualitative data will be gathered from organizational staff at four points. Qualitative interviews with clinicians and peer recovery support staff will occur during the intervention phase. The goal of the interviews is to gain a better understanding of patterns with app adoption and use. Phone interviews of up to 30 minutes will be conducted with approximately 15 people at various sites. The interviews will be audiotaped (with participant permission), but the staff person's identity will be protected and in no way be linked to results.

Additionally, the study, interviews with staff from a randomly selected site in all organizations will occur at the end of intervention phase and again at the same site at the end of sustainability phase. The intent of the surveys is to gain a retrospective understanding of what occurred during implementation. Phone interviews of up to 30 minutes will be conducted with up to four people in at each site. The interviews will be audiotaped (with staff participant permission), but the staff person's identity will be protected and in no way be linked to results.

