Analysis of Supplemental COVID-19 Patient Survey and In-Depth Interview Data: Patient survey data will be matched with longitudinal app usage data. We anticipate using linear regression models to quantify the association between app usage (modeled continuously and binary as an indicator of meaningful use of A-CHESS) and several continuous outcomes based on validated measure – anxiety (PROMIS 29) and loneliness (UCLA Loneliness Scale-8). We will adjust for potentially confounding variables, including socio-demographic characteristics, recovery capital, criminal justice involvement, and substance use disorder severity. Further, we will use logistic or log-binomial regression models to assess how app usage is associated with substance use disorder treatment participation (e.g., AA/NA/self-help group participation, attendance at group therapy).

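### The COVID-19 survey models adjust for severity and recovery capital measured after app use began, so the coefficient may omit part of any benefit and cannot be read as the total association

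*Combined protocol and SAP*

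**What the plan says.** The paragraph of Section 9 on the supplemental COVID-19 data plans linear regressions to "quantify the association between app usage (modeled continuously and binary as an indicator of meaningful use of A-CHESS", with anxiety and loneliness as outcomes. The exposure comes from server logs: "Patient survey data will be matched with longitudinal app usage data". On covariates it states: "We will adjust for potentially confounding variables, including socio-demographic characteristics, recovery capital, criminal justice involvement, and substance use disorder severity". It gives no model without these covariates, no sensitivity analysis, and no rule placing the counted usage before the survey.

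Table 1 in Section 5 lists alcohol use disorder severity, "Substance Use Disorder Severity", recovery strengths, loneliness and anxiety under a single instrument, timed as "Patient COVID-19 Survey – once during March 2021". Section 7 also places these measures in that one survey. Section 5 (Study Design, consumer level) sends it to everyone who has opened an A-CHESS account, 520 people at the time of writing.

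The purpose is stated three times. The introduction wants to know how A-CHESS mitigates anxiety and loneliness. Section 2 asks whether using it may help patients manage them. Section 7 asks how use may have lessened the impact of the pandemic on them.

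**The concern.** A confounder precedes the exposure, or at least is not changed by it. Here the plan gives that role to two variables recorded after exposure began, at the same sitting as the outcomes. If app use lowers severity, and lower severity eases anxiety or loneliness, then holding severity fixed takes that route out of the coefficient. What is left is the association that does not run through current severity or recovery, which is narrower than the question in Section 2.

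The practical risk is a misread null. An adjusted coefficient near zero could be reported as no benefit even if the app had worked by reducing substance use. With only one model planned, the report would contain nothing to show the difference.

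**Working it through.** The plan states no effect size, power or standard deviation for these models, so there is no figure of its own to reproduce. The check has two parts: the timing and roles of the variables, and an illustration of how far the estimate could move.

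**Timing.** Respondents hold accounts before they are surveyed, so use started before severity and recovery strengths were recorded. No pre-app measure of either that could be linked to the survey is named. The state data listed in Section 5 are de-identified and include no severity measure. Section 9 says recovery capital and Table 1 says recovery strengths; treating them as the same is an inference, but no other listed measure fits.

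**Could use change the covariates?** For severity, Section 1 gives a reason to think so: in an earlier randomized trial, A-CHESS patients "reported 51% fewer risky drinking days in the prior 30 days" (means 1.39 and 2.75), with higher abstinence at 8 months (78% vs. 67%) and 12 months (79% vs. 66%). No effect on recovery strengths is reported.

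**Could the covariates also carry confounding?** Yes. Amount of use is chosen by the patient and may depend on severity at entry, of which survey-time severity is a proxy.

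**Exposure window.** Section 5 (Use data) collects frequency of use for 12 months from first use. For a patient who started after March 2020, that window runs past a March 2021 survey, so use after the outcome could be counted.

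**Size by hand.** Let a be the effect of use on severity, b that of severity on anxiety, and c the direct effect. Total = c + a·b, and the share removed by holding severity fixed is a·b / total. All values are assumptions. With the total set at -0.20:

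| a | b | a·b | share of -0.20 |
|---|---|---|---|
| 0 | any | 0 | 0% |
| -0.10 | 0.30 | -0.03 | 15% |
| -0.20 | 0.40 | -0.08 | 40% |
| -0.30 | 0.50 | -0.15 | 75% |

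**Size when severity has both roles.** Linear model, 2,000,000 simulated records per row, least squares. U is pre-app severity; use A has unit variance and depends on U with coefficient g. Survey severity M = r·U + a·A + error (SD 0.6), with r = 0.6 when g = 0 and 0.7 otherwise. Anxiety Y = c·A + b·M + h·U + error (SD 0.8). Assumed throughout: b = 0.40, c = -0.10; a = -0.20 or 0; h = 0 unless shown. With a = -0.20 the true total is -0.10 + (-0.20)(0.40) = -0.18.

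| Scenario | True total | No severity term | Pre-app severity | Survey-time severity |
|---|---|---|---|---|
| 1. Pure mediator, g = 0 | -0.18 | -0.180 | -0.180 | -0.099 |
| 2. a = 0, g = 0 | -0.10 | -0.099 | -0.099 | -0.100 |
| 3. a = 0, g = 0.3 (sicker use more) | -0.10 | -0.017 | -0.101 | -0.101 |
| 4. a = -0.20, g = 0.3 | -0.18 | -0.094 | -0.179 | -0.098 |
| 5. a = -0.20, g = -0.3 (healthier use more) | -0.18 | -0.264 | -0.180 | -0.100 |
| 6. As 4, h = 0.3 | -0.18 | -0.006 | -0.180 | -0.012 |
| 7. As 5, h = 0.3 | -0.18 | -0.355 | -0.181 | -0.094 |
| 8. As 1, plus an unmeasured common cause of M and Y (0.5 on each) | -0.18 | -0.180 | -0.180 | -0.049 |

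In row 1 the planned adjustment loses about 0.08/0.18 = 44%. In rows 2 and 3 it loses nothing, and in row 3 it removes real confounding that the model without severity leaves in. In rows 6 and 8 it does not recover even the direct effect of -0.10. In rows 4 and 6 both feasible models (no severity term, survey-time severity) fall short of -0.18, so the pair need not bracket the truth.

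**The case against.** The strongest reply is that Section 9 promises only an association, that use is self-selected, and that leaving severity out could do more harm than including it. The last part stands: without a severity term the estimates above run from -0.006 to -0.355 against a true -0.18. Severity should not simply be dropped. The first part helps less, because the aims ask about benefit and adjusting for confounding is already a causal step.

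A reader might infer that the planned models definitely strip out part of the benefit. The documents do not show that. The earlier trial compared the app with a control group, whereas here every respondent has an account and the exposure is amount of use. No figure links severity to anxiety or loneliness. No recall period is given for the severity instruments, and Section 5 says patients also report their substance use and treatment history, so the measures may partly reflect status before the app.

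A reader might also infer that the weekly check-ins supply a ready baseline. They do not. Section 5 says: "With subsequent use of the A-CHESS app patients will be asked how they are doing and about their recent alcohol and drug use". They follow first use and are voluntary, and low users are the likeliest to lack one. Sections 4 and 9 describe linking usage data, not check-in answers.

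Finally, the point should not be carried over to the treatment-participation models, for which Section 9 states no clear adjustment set.

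**Conclusion.** The concern holds in a limited form. Severity and recovery capital are entered as confounders, although their only listed measures are taken with the outcomes, after use began. Severity at least may partly result from use. The planned coefficient therefore cannot be read as the total association of A-CHESS use with anxiety or loneliness, and a null would not show lack of benefit.

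The size cannot be derived from the documents. Under the assumed paths the share removed runs from 0% to 75% in the hand calculation, and is 44% in the pure-mediator simulation. Because the covariates also proxy for pre-app severity, the net bias is unknown. The conclusion rests on recovery capital meaning the recovery strengths item and, for any loss to occur, on use changing severity or recovery strengths and these in turn affecting the outcomes.

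Only the supplemental observational aim is touched; the randomized comparison is unaffected.

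**What to change.** For anxiety and loneliness, prespecify two models and report them side by side:

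- (a) adjusted only for characteristics fixed before app use: socio-demographics and criminal justice history before enrolment. Items that can change later, such as employment or housing, should be assigned explicitly to (a) or (b).
- (b) the planned model, adding survey-time severity and recovery capital, interpreted as the association not acting through current severity or recovery. That reading assumes no unmeasured common cause of these covariates and the outcomes.

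State that a null in (b) alone is not evidence of no benefit, that (a) leaves confounding by pre-app severity, and that the two need not bracket the true effect. Count only app use before each respondent's survey date. If check-in answers can be linked, add the earliest one as a sensitivity analysis only, noting that it follows first use and that its missingness may depend on use.

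The cost is a rewritten paragraph, one more reported model, and residual confounding in (a) that has to be acknowledged. No new data collection is needed.

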10. RECORDS TO BE KEPT

- Organizational traits
- Patient/counselor traits
- Survey results (Organizational and staff surveys, COVID-19 surveys)
- A-CHESS Server data specific to project

- IDPH data

Appendix A: CHESS DATA SECURITY PLAN

In accordance with the Health Insurance Portability and Accountability Act (HIPAA), CHESS has adopted the following Data Security and Monitoring Plan:

Data Security Officer. [name] is the primary security officer for CHESS. Responsibilities of the security officer includes: developing information technology (IT) security policies, increasing security awareness for all CHESS staff, providing virus protection for IT resources, maintaining security patches on computing equipment, developing and implementing back-up procedures, performing periodic vulnerability scanning on IT equipment, reviewing and updating firewall strategies and policies, and enhancing the physical security of IT resources.

Training. Before gaining access to our data, all of our students, faculty and staff must provide our Data Security Officer a copy of their certificates of completion of the UW-Madison Human Subjects online training

(<http://info.gradsch.wisc.edu/research/compliance/humansubjects/tutorial/>) and the online HIPAA Privacy Rule training: <http://www.wisc.edu/hipaa/ResearchGuide/index.html>.

Furthermore, they are required to complete training on CHESS security procedures and policies and sign a “CHESS Data Security Policy Certification” upon completion of this training.

Workstation. All workstations will require login with a unique user name and password. Users will log-out from or lock workstations when leaving them unattended. Screen savers will be configured to require a password to activate after 10 minutes of workstation inactivity. Users requiring virtual private network (VPN) access to the CHESS network will only do so with computers specifically certified by a CHESS Data Security Officer.

Passwords. Users require a password to access any computer connecting to the CHESS network. Passwords may not contain all or part of the user's account name and must be at least 7 characters long. Passwords may contain characters from 3 of the following four categories: English uppercase characters (A through Z); English lowercase characters (a through z); base 10 digits (0 through 9); non-alphanumeric characters (e.g., !, \$, #, %). User accounts will be locked after 5 failed login attempts and will reactivate automatically after 30 minutes of no failed attempts. Passwords may not be stored in proximity to the workstation and may not be shared by others.

Data created by subjects as they use ACHESS. Data are not stored on smartphones, so there is no danger if a subject's phone is stolen. Hackers could obtain data from the server, but user-identifying data are not stored on servers. We do not ask for identifying information (e.g. addresses, phone numbers) on ACHESS. Users receive code names and passwords. Users could walk away from their phone and not log out, leaving sensitive information on screen. We warn users (on enrollment, during training, and when they use the services) to not share personal data in the on-line discussions or ask-an-expert service and to close the browser if they leave ACHESS. All dynamic pages are configured so the browser stores a local copy only when they appear on screen. Cookies last only for the duration of the session. We use encryption software on our system so the website will be secure.

Storage, Retrieval, and Disposal of Protected Information. Any computer-based Consumer Identifiable, Confidential, or Personnel Data will be stored on secure servers only and may not be stored on individual workstations. Currently, the only place such information can be stored is a secured section of the CHESS Intranet. Servers within CHESS will be located in locked rooms with limited access. The CHESS Data Security Officer will be responsible for assigning and restricting access to shared resources on the CHESS servers. Consumer Identifiable,

Confidential, and Personnel Data may not be copied to or stored on CHESS publicly accessible servers at any time. Remote access to files on secure CHESS servers may be provided only through a virtual private network (VPN) on a certified CHESS Workstation (See CHESS Workstation policy above for details). Storage media will be rendered unusable before disposal. All back-up media will be stored in locked rooms with limited access.

Sending data by fax. All correspondence via fax must be stripped of consumer identifiers. The sender must call the receiver to ensure the receiver is available to receive the fax.

10. ACRONYM LIST

ACHESS	Addiction Comprehensive Health Enhancement Support System
CBT4CBT	Computer Based Training for Cognitive Behavioral Therapy
CFIR	Consolidated Framework for Implementation Research
CHESS	Center for Health Enhancement System Studies
ICC	Intraclass correlation
IDPH	Iowa Department of Public Health
IRHIT	Iowa Rural health Information technology Initiative
NIATx-TI	Network for the Improvement of Addiction Treatment-Technology Implementation
N-SSATS	National Survey of Substance Abuse Treatment Services
OCM	Organizational Change Manager
PDSA	Plan-Do-Study-Act
RCT	Randomized Control Trials
RE-AIM	Reach, Effectiveness, Adoption, Implementation, Maintenance
RIS	Readiness for Implementation (of Technology)
SDT	Self-Determination Theory
SUD	Substance Use Disorder
TAM	Technology Acceptance Model
TAU	Treatment as Usual
TEDS	Treatment Episode Data Set
TES	Therapeutic Education System

